#### F. Adverse Events

**1) Assessing Events:** As described in section VI.A., we will assess for adverse events at every study visit. For participants who are prescribed varenicline through the study clinician, this will include queries about potential side effects to varenicline using a standardized checklist in addition to the C-SSRS for suicide risk assessment weekly through week 8 and every other week through week 12.

Participants will also be reminded to report problems, whether related or potentially related to study participation or not, to study personnel between scheduled intervention visits and assessments. They will be instructed on how to contact study personnel should problems occur during intervals between visits. Adverse events will be documented, carefully assessed to determine expectedness, relatedness, and potential for harm, and steps will be taken to prevent future similar events from occurring. Violations of participant privacy/confidentiality will be treated as an unanticipated problem related to the study and will be considered reportable.

**2) Reporting of reportable events to the IRB:** We will adhere to the Mass General Brigham policy statement on “Reporting Unanticipated Problems including Adverse Events.” Consistent with this policy, an adverse event will be defined as “any untoward or unfavorable medical occurrence in a human subject, including any abnormal sign, symptom, or disease, temporally associated with the subject’s participation in the research, whether or not considered related to the subject’s participation in the research.” A serious adverse event will be defined as an adverse event that results in death, is life-threatening, requires hospitalization, causes persistent or significant disability, or requires medical or surgical intervention. The PI and his designated study staff will be responsible for the monitoring of adverse events in study participants.

Adverse events reported to the PI or other study staff will be documented in an adverse event report containing a description of the event, the date and time of onset, the date and time of resolution, the expectedness of the event, the relationship to the study, the seriousness of the event, and the action taken in response to the event. An adverse event will be deemed

unexpected if the nature, severity, or frequency of the event is not consistent with a known or foreseeable risk given the research procedures, the characteristics of the subject population, or with an expected progression of an underlying condition. The following attribution scale will be used to describe the relationship of the adverse event to the study protocol: unrelated, possibly related, or related to the protocol.

Unexpected adverse events that are at least possibly related to the research and suggest the research puts participants at increased harm will be reported to the Mass General Brigham IRB and Data and Safety Monitoring Board (DSMB; see section H below) within 5 working days or 7 calendar days. Serious adverse events that are unexpected and at least possibly related to the research will be assumed to suggest that the research puts participants at increased risk of harm and will be reported to the Mass General Brigham IRB and DSMB within the same time frame. Any action resulting in a temporary or permanent suspension of this study will be reported to the NIH funding agency's program official. A summary safety report detailing all adverse events and their handling will be included in annual study progress reports to the Mass General Brigham IRB (if requested) and the NIH funding agency. Adverse event reports and annual safety summaries will be documented by study ID number; personal identifiers will not be included in these reports.

**3) Reporting mechanisms to NCI and DSMB:** The PI will report reportable events to the NCI Project Officer by phone or email within 5 working days and follow-up with a written report (by fax or email) within 10 calendar days, detailing any additional information and whether or not the event is related to participation in the study or may affect future participation in the study.

The PI will make a report to the Chairperson of the DSMB within 5 working days of learning of the event. The DSMB will review the event (usually on the phone or via email) and make a report via email to the PI, who will forward the report to the IRB and NCI Project Officer.

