### B. Preliminary data

In October 2015-June 2016, we conducted a pilot RCT of financial incentives for smoking abstinence among homeless smokers at BHCHP. Participants were offered 8 weeks of transdermal nicotine patches and 8 15-minute sessions of behavioral counseling, with (N=25) or without (N=25) escalating financial rewards for brief smoking abstinence, defined as an exhaled CO level <8 ppm. After randomization, participants were asked to make 14 assessment visits over 8 weeks: 3 times per week during weeks 1-2, 2 times per week during weeks 3-4, and once per week during weeks 5-8. Control arm participants received a \$10 payment at each visit, regardless of whether they were abstinent. Incentive arm participants received a payment only if they were abstinent. Payments began at \$15 and increased in \$5 increments with each successive abstinent measurement, up to a maximum of \$35. Non-abstinence or non-attendance resulted in no payment and reset subsequent payments to the starting value of \$15. Payments were issued electronically in real-time onto study-supplied debit cards that could be used at any retail outlet. The primary outcome was a repeated measure of CO-defined abstinence (CO <8 ppm) across the 14 assessment visits. Sensitivity analyses incorporated self-reported abstinence duration.

Two-thirds of eligible individuals participated in the RCT, and we reached our target enrollment within 6 months. Participants attended a median of 10 (of 14) assessment visits, with 98% attending  $\geq 1$  visit and 78% attending  $\geq 7$  visits. Across all 14 time points, CO-defined smoking abstinence was substantially higher in the incentives arm than in the control arm (ranges: 32-68% vs. 0-20%; overall OR 7.28, 95% CI 2.89-18.3; Figure 1). At 8 weeks, 48% of incentive arm participants and 8% of control arm participants had an exhaled CO <8 ppm ( $P=0.004$ ; Figure 2). In a sensitivity analysis incorporating self-report of not smoking all or part of a cigarette in  $\geq$

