#### F. Electronic Communication

The Twilio text messaging feature will be integrated into our REDCap database. This will allow study staff to send participants automated text message reminders about their next scheduled appointment and the maximum potential payment they can earn at this visit. Text messages will not include any identifying information and participants can opt out at any time by texting the word “STOP” (see Appendix 1 for sample text messages). Participants must consent to receive these text messages. The consent form includes information outlined in the Mass General Brigham guidelines for texting research subjects.

Study staff may use Mass General Brigham’s HIPAA-compliant video conference platforms, Microsoft Teams or Enterprise Zoom, to administer surveys and complete coaching sessions as part of the team’s in-person remote COVID-19 safety protocol (see section V.A). Participants who prefer this form of engagement will arrive to the BHCHP clinic where on-site study staff will set up a Teams or Zoom call on a study tablet for the participant to use. Participants will participate in the video call using headphones in a private or semi-private space within the clinic; study staff will administer the survey or complete the coaching session via Teams or Zoom either on-site (in a separate room) or remotely. This will minimize in-person contact between study staff and participants while allowing participants and study staff to engage in potentially sensitive conversations during the surveys and coaching sessions. For safety and security, no Teams or Zoom links will be shared with participants. Teams or Zoom meetings will require passwords and will not be shared with anyone other than study staff. Participants will be instructed not to use the chat function during these meetings as the feature is not encrypted. Participants will also be advised that photographs and recordings of Teams or Zoom calls are not allowed.

Participants may meet with the study clinician via MGB-hosted Microsoft Teams, MGB Enterprise Zoom, or BHCHP's Epic/OCHIN integrated HIPAA-compliant Zoom platform. The third option allows participants to engage with the clinician in the manner currently used to provide COVID-safe virtual clinical care at BHCHP.

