- Suicidal thoughts, intention, and behaviors since last study visit, as measured by a modified version of the C-SSRS (if applicable; every monitoring visit).
- Other adverse events not related to varenicline if reported by participant (every monitoring visit)
- All items italicized in the baseline survey table above at 12 weeks, or within 2 weeks post
- Saliva cotinine level from results of laboratory cotinine testing at 12 weeks, or within 2 weeks post

**4) Post-treatment outcome assessment visit data elements:** The following variables will be collected at 24 weeks, or within 2 weeks post, unless otherwise specified in parenthesis.

- Point-of-care saliva cotinine level (incentive participants only)
- Date and time last smoked all or most of a cigarette
- Date and time of last puff of a cigarette
- Number of smoking days in the past 7 days
- Number of quit attempts in the past 3 months
- Use of cessation aids
- Use of vape or e-cigarette in the past 7 days
- Use of other tobacco products in the past 7 days
- All items italicized in the baseline survey table above
- Laboratory saliva cotinine level

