## B. Study Endpoints

**1) Primary outcome:** The Aim 1A outcome is saliva cotinine-verified 7-day smoking abstinence at 12 weeks. Participants who report not smoking in the past 7 days and have a saliva cotinine level of <10 ng/mL at the week 12 timepoint will be considered abstinent.

**2) Secondary outcome:** The Aim 1B outcome is 7-day smoking abstinence at 24 weeks, based on self-report and verified by a salivary cotinine level of <10 ng/mL.

**3) Other outcomes:** Other outcomes include 7-day smoking abstinence at weeks 1-11 (defined as no smoking the past 7 days and having a point-of-care saliva cotinine level <30 ng/ml), use of varenicline or other smoking cessation medications (assessed by self-report and BHCHP chart review), use of other tobacco treatment resources, changes in past-month drug and alcohol use and psychiatric symptoms (assessed with the AUDIT, DAST-10, drug use inventory, PHQ-9, GAD-7, at 12 and 24 weeks).

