Study staff will also proactively assess suicidality at every on-treatment monitoring visit using a modified version of the C-SSRS (see Appendix 3). Participants at low risk for suicide based on the C-SSRS will be made aware of available behavioral health care resources, including crisis line numbers and on-site mental health services at BHCHP. Participants at moderate risk for suicide based on the C-SSRS will be given 24-hour crisis line numbers and encouraged to schedule a visit with their PCP or an on-site behavioral health provider within 2 business days, with assistance from study staff. The study clinician or PI will call these participants within 24 hours to discuss their suicidality and reinforce the above evaluation plan. Participants at high risk for suicide based on the C-SSRS will be escorted immediately to the on-site BHCHP clinic for an urgent mental health evaluation by BHCHP clinical staff. Study staff will advise these participants to stop varenicline. The study clinician and PI will be notified and will follow-up with

the participant within 24 hours to discuss the plan for moving forward. In instances in which participants show moderate or high risk of suicide based on the C-SSRS, study staff will communicate with participants' PCPs via secure Epic messaging regarding the outcome of this assessment within 2 business days (if moderate risk) or within 24 hours (if high risk). Although suicidality will not be proactively assessed during tobacco coaching sessions, if participants spontaneously bring up suicidal thoughts, the tobacco coach will follow similar procedures to the monitoring visits and assess suicidality risk using the modified C-SSRS and react accordingly based on level of risk.

If a participant misses their monitoring visit, this will trigger an automated text message to their study phone or personal phone advising them to call study staff if they are experiencing any side effects or other concerns related to their participation in the study (see Appendix 1).

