If a participant calls study staff with concerns, study staff will make a note of any reported side effects and their severity in a manner similar to that which would occur during an in-person monitoring visit. However, to improve the efficiency of phone encounters, reduce the use of participants' cell phone minutes and allow the participant to direct the conversation in a more fluid way, a complete checklist of side effects and the C-SSRS scale will not be administered by default during these phone calls unless dictated by participants' reported symptoms. If a participant reports mental health concerns, this will prompt administration of the (C-SSRS) over the phone, with triage according to the algorithm outlined for in-person monitoring visits.

Psychological status (including depression and anxiety symptoms) will be formally assessed at baseline, and at 12 and 24 weeks, providing additional opportunities to identify and address any psychological discomforts that participants may be experiencing. If any participant screens positive for any mental health disorders listed, study staff will ask participants whether they are currently receiving behavioral health care and assist them with connecting or reconnecting with such care, either at BHCHP or at an outside facility (if preferred by the participant).

Study staff will be trained to recognize the signs of an intoxicated participant and to activate a response plan appropriate to the level of symptoms or impairment. Participants demonstrating evidence of mild substance intoxication will be informed of on-site behavioral health services to address substance use. Participants with more profound levels of intoxication causing substantial impairment in functioning and well-being will be referred for immediate on-site medical evaluation. The clinic at BHCHP headquarters has walk-in medical and behavioral health appointments available every weekday to support the on-site referrals described above.

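### Planned adverse event capture depends on the participant attending or making contact, so hospitalisations and deaths can be missed in those who stop attending, especially between weeks 12 and 24

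*Combined protocol and SAP*

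**What the plan says.** Section IX.F.1 commits the trial to regular assessment: "we will assess for adverse events at every study visit". For participants prescribed varenicline by the study clinician, this includes a side-effect checklist and the C-SSRS, weekly to week 8 and every other week to week 12. Between visits the plan relies on the participant: "Participants will also be reminded to report problems, whether related or potentially related to study participation or not, to study personnel".

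The data list for monitoring visits (VI.A.3) takes events unrelated to varenicline only when volunteered: "Other adverse events not related to varenicline if reported by participant (every monitoring visit". The list for the 24-week visit (VI.A.4) has no adverse event item.

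When a monitoring visit is missed, IX.C says that "this will trigger an automated text message to their study phone or personal phone advising them to call study staff" if they have side effects or other concerns. If the participant calls, "a complete checklist of side effects and the C-SSRS scale will not be administered by default during these phone calls", unless the reported symptoms call for them.

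IX.F.2 counts death and hospitalisation among serious adverse events, and its definition of an adverse event does not require relatedness to the study. IX.H has the DSMB monitor safety through adverse event reports.

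The chart is already in use. Every participant must have a BHCHP primary care provider (III.A, inclusion criterion 6), staff complete a chart review form before randomisation (V.A.2), and VI.B.3 lists as an outcome "use of varenicline or other smoking cessation medications (assessed by self-report and BHCHP chart review").

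**The concern.** Each planned route starts with the participant coming in or getting in touch. Someone who has died cannot do either, and someone in hospital or out of contact may not. The events most likely to be lost this way are among those the plan classes as serious.

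The plan foresees loss to follow-up for efficacy (VI.C counts a missing outcome as non-abstinent) but has no counterpart for safety. IX.E rules out a formal interim analysis and early-stopping rules, so the DSMB's view of safety rests largely on the event reports it receives. Nobody can judge the relatedness or expectedness of an event that staff never learn of.

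**Working it through.** The plan states no figure on this point, so the check is a reading of the capture routes, followed by an illustration of size.

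**Routes, side by side**

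| Route | Section | What it needs |
|---|---|---|
| Assessment at study visits | IX.F.1, VI.A.3 | Participant attends |
| Reminder to report between visits | IX.F.1 | Participant makes contact |
| Automated text after a missed visit | IX.C | Participant receives it and calls |
| Report from a provider or another person | IX.F.2 does not restrict who reports | Someone else volunteers it |
| Chart search, vital-status check, or call to a provider to find events | None | Not planned |

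The fourth route is open but passive. The weekly data review in IX.A looks for missing data and recording problems, not for events.

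**Timing.** Monitoring visits run from week 1 to week 12, and the next outcome visit is at week 24. The interval is 24 - 12 = 12 weeks, half of the 24 weeks after the quit date. It contains no monitoring visit, and the visit that closes it has no adverse event item in VI.A.4, although IX.F.1 covers every study visit and points to VI.A for how this is done.

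**Attendance.** The only attendance figures come from the pilot (I.B): "Participants attended a median of 10 (of 14) assessment visits", so the median participant missed 4/14 = 29%. In the same pilot 78% attended at least 7 visits, so 100% - 78% = 22% attended fewer than half. These figures pool both arms and come from a different schedule (14 visits in 8 weeks). They show that missed visits are common. They are not a drop-out rate, and a missed visit is not a missed event.

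**Illustration of size.** The documents give neither a serious-event risk nor a share out of contact, so all three inputs below are assumptions. Let r be the overall serious-event risk, m the share of the 180 participants out of contact, and k their risk relative to the others. If every event in those out of contact goes unseen and every other event is seen:

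- share unseen = m·k / [(1 - m) + m·k]
- number unseen = 180·r × share unseen

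| r | m | k | True events | Share unseen | Events unseen |
|---|---|---|---|---|---|
| 5% | 10% | 1 | 9 | 10% | 0.9 |
| 10% | 22% | 1 | 18 | 22% | 4.0 |
| 10% | 22% | 2 | 18 | 0.44/1.22 = 36% | 6.5 |
| 20% | 30% | 2 | 36 | 0.60/1.30 = 46% | 16.6 |

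The 22% is borrowed from the pilot share above. Across r of 5-20%, m of 10-30% and k of 1-2, the range is about 1 to 17 events, or 10% to 46%. Passive reports, or a return to contact, would lower these numbers.

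**By arm.** Monitoring-visit pay differs (V.A.6). A control participant receives $10 whatever the result. An incentives participant receives $25 to $70 for a negative test and nothing for a positive one. Non-abstinent incentives participants thus have less reason to attend than controls, and abstinent ones have more. The documents give no attendance by arm, so the net direction cannot be stated.

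**The case against.** The strongest reply is that capture is broader than it first looks. IX.F.2 documents events reaching the PI or staff without limiting who reports them. The PI is a BHCHP physician, and primary care providers are told of enrolment and invited to respond. Surveys, coaching and clinician visits can be remote (V.A). The C-SSRS asks about the time since the last study visit, so a later visit can recover earlier events. The 24-week survey repeats general health, chronic-condition and mental-health measures. Varenicline is supplied in one-month allotments, which limits exposure in those who stop coming. All of this stands. It means that events can be missed, not that they always are. It does not supply a procedure for the participant who never returns, and the adverse event definition is not confined to drug effects.

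Four stronger readings are tempting, and the documents do not support them:

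- **Events are recorded only when the participant reports.** Passive reports from others are possible; they are simply not sought.
- **The between-arm safety comparison is biased in a known direction.** VI.B and VI.C plan no adverse event comparison by arm, and attendance could differ either way. A risk ratio built on assumed detection rates would measure the assumptions.
- **The shortened phone assessment contradicts the scheduled checklist and C-SSRS.** IX.C describes unscheduled calls made by the participant; nothing says such a call replaces a visit. Staff still record side effects and severity, and mental health concerns prompt the C-SSRS.
- **The missed-visit text should be exempt from opting out.** V.F requires consent to texts and says "participants can opt out at any time by texting the word" STOP. An exemption would conflict with that promise. Calling emergency contacts could disclose participation to third parties, and a chart check needs neither step.

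**Conclusion.** The gap is real but narrow: no planned procedure seeks hospitalisations or deaths in participants who stop attending, and the exposure is greatest between weeks 12 and 24. This follows from the text and needs no assumption. The size is unknown. The range of about 1 to 17 unseen events among 180 rests wholly on the assumed risks and contact rates and on the simplification that no event in those out of contact comes to light. Detection may differ by arm, in a direction the documents do not settle. Sample size, significance level and power are unaffected. The change is worth making because it is cheap and would make capture of chart-recorded serious events independent of attendance.

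**What to change.** 1. In IX.F.1, add: *At weeks 12 and 24, staff will review the BHCHP chart of every randomised participant, whether or not they attended and by the same method in both arms, for hospitalisation, emergency visit or death since randomisation. Events found will be recorded as adverse events with their source.*
2. In VI.A.4, add an adverse event item to the 24-week data list, so that it agrees with IX.F.1.
3. Report by arm the share of scheduled safety assessments completed, so that readers and the DSMB can see how complete the event counts are likely to be.

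Cost: a short amendment and 180 charts reviewed twice (180 × 2 = 360 reviews) by staff who already use this record. VI.B.3 does not fix the timing of its chart review, so the two time points may be additional work. Each event found needs the full report described in IX.F.2. The sponsor should confirm that the consent covers this use of the chart. Events treated elsewhere will be captured only if they reach the BHCHP chart, and the report should state that limit.
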